3.3 Exclusion criteria

Patients who meet any of the following exclusion criteria will be excluded. Laboratory tests to determine exclusion criteria will be performed at a central testing facility. If blood pressure measurements or a given laboratory test is performed multiple times during the screening period, the most recent test will be used for determination.

- (1) Patients with anaemia resulting primarily from a disease other than CKD after date of consent (e.g., sickle-cell syndrome, myelodysplastic syndrome, myelofibrosis, haematopoietic malignancy, myeloma, haemolytic anaemia, thalassemia, or aplasia pure red cell)
- (2) Patients with active haemorrhaging or exsanguination within 8 weeks prior to the first day of the screening period.

- (3) Patients who have received RBC transfusion within 8 weeks prior to the first day of the screening period.
- (4) Patients who have received testosterone enanthate or mepitiostane within 8 weeks prior to the first day of the screening period.
- (5) Patients determined by investigators/subinvestigators to likely require immediate rescue therapy or drug holiday of the study drug after initiation of treatment period.
- (6) Patients with AST, ALT, or total bilirubin values of 2.5 times or greater the upper limit of standard during the screening period. This does not apply to patients with Gilbert's syndrome.
- (7) Patients with uncontrolled hypertension (defined as systolic BP >180 mmHg or diastolic BP >110 mmHg) during the screening period or on the first day of the treatment period.
- (8) Patients for whom any of the following apply upon fundoscopy during the screening period:
 - ✓ No ocular fundus findings are possible.
 - ✓ Active ocular fundus disease.
- (9) Patients with severe cardiac failure from the day of consent (Class IV according according to severity classification of the New York Heart Association (NYHA))
- (10) Patients with cerebrovascular disorders or acute coronary syndromes (hospitalization for unstable angina or myocardial infarction, etc.) within 12 weeks prior to the first day of the screening period. Patients who have been hospitalized due to acute coronary angioplasty or cardiac failure.
- (11) Patients with malignant tumors or a history of such. However, this does not apply to patients with no relapse for 5 or more years (5 or more years with no relapse from last administration of chemotherapy if chemotherapy was used).
- (12) Patients with incidence or relapse of deep vein thrombosis or pulmonary embolism within 12 weeks prior to the first day of the screening period.
- (13) Patients with current or previous haemosiderosis or hemochromatosis.
- (14) Patients with a history of or plans for organ transplant (not including being on a waiting list for renal transplant), haematopoietic stem cell transplant, or bone marrow transplant.
- (15) Patients with an allergy to the study drugs.
- (16) Patients who have participated in another clinical study and received study drugs within 12 weeks prior to informed consent, or within 5 times the half-life of the study drug (whichever is longer).
- (17) Patients who have previously used MT-6548.
- (18) Patients with known low tolerance to HIF-PH inhibitors.
- (19) Patients who are unwilling to consent to use contraception from the beginning of the study period to 30 days following the final dose of the study drug for women who may become pregnant, or from the beginning of the study period to 90 days following the final dose of the study drug for men.

- (20) Female patients who are or may be pregnant, or women who are nursing.
- (21) Other patients judged by investigators/subinvestigators to be inappropriate as a subject in this study.

Rationale

- (1)–(4) These were considered likely to affect drug efficacy evaluation of MT-6548.
- (5)–(15) (18) Set in regard for patient safety and ethics.
- (16) Set in regard to ethical performance of study. Also, unevaluated drugs may affect efficacy or safety in unpredictable ways.
- (19) (20) Reproductive and developmental toxicity safety has not been established in humans, and the possibility that the study drug may transfer to human sperm cannot be ruled out. Therefore, this was set for safety reasons.
- (21) Set in order to allow determinations regarding study participation in regard for patient safety for reasons other than the general factors listed above.

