3.4 Re-testing/re-screening

(1) Re-testing

Re-testing during the screening period may be performed at the discretion of investigators/subinvestigators for subjects who did not meet inclusion criteria, or who met exclusion criteria, for reasons such as laboratory values (Hb, eGFR, serum ferritin, TSAT, folic acid, vitamin B₁₂, AST, ALT, or total bilirubin) or blood pressure.

Subjects with blood pressure measurements on the first day of the treatment period which meet exclusion criteria may be re-tested at the discretion of investigators/subinvestigators, and processed for treatment period initiation if they no longer meet exclusion criteria.

However, the maximum time from the first day of the screening period to the first day of the treatment period is 6 weeks.

(2) Re-screening

Re-screening may be performed at the discretion of investigators/subinvestigators if subjects who did not meet inclusion criteria, or who met exclusion criteria, for reasons such as laboratory values (Hb, eGFR, serum ferritin, TSAT, folic acid, vitamin B₁₂, AST, ALT, or total bilirubin), blood pressure, or blood pressure on the first day of the treatment period, may have become eligible for the study due to natural course or drug treatment.

However, re-screening may only be performed once for any given subject.

4. Explanations to subjects and consent

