5.2 Study design

The current study is a multicenter, randomized, open-label, active-controlled, parallel group comparative study.

(1) Screening period

The screening period begins on the first day of the screening period, and ends upon completion of tests required on the first day of the treatment period. Maximum screening period time is 6 weeks. Two visits will be made during the screening period; the first (SV1) is the first day of the screening period. The second screening period visit (SV2) occurs after results from laboratory tests performed on the first day of the screening period have been obtained. Re-testing will be performed as necessary.

(2) Treatment period

The treatment period will last from completion of scheduled tests on the first day of the treatment period to completion of blood sampling for haematology tests on the final day of the treatment period (Week 52 of the treatment period or discontinuation of treatment).

The treatment period consists of phase 1 and phase 2, as defined below.

- ✓ Treatment period Phase 1: From completion of scheduled tests for the first day of the treatment period to completion of scheduled tests for Week 24 of the treatment period
- ✓ Treatment period Phase 2: From completion of tests specified for Week 24 of treatment period to completion of tests specified for Week 52 of treatment period

Treatment period study visits will be made every 2 weeks up until Week 12, and every 4 weeks thereafter for scheduled tests. However, study visits may be more frequent if variation in Hb levels causes concern for excessive increase or decrease in Hb, if the dose interval for darbepoetin alfa injection is shorter than the study visit interval, or for other reasons.

(3) Follow-up observation period

The follow-up observation period consists of 2 weeks from completion of blood sampling for haematology tests on the final day of the treatment period. The final day of the follow-up observation period is 2 weeks from the completion of blood sampling for haematology tests on the final day of the treatment period, regardless of whether a study visit is made on that day.

Subjects should make study visits as close to the same time as possible during the study period for scheduled tests.

Rationale

Screening period: Established to confirm subject suitability for the study.

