8.5 Concomitant medications and therapies and rescue therapy

8.5.1 Prohibited concomitant medications and therapies

(1) ESA formulations

Concomitant use of epoetin alfa (recombinant), epoetin beta (recombinant), darbepoetin alfa (recombinant), and epoetin beta pegol (recombinant) is prohibited for the period described below. This excludes darbepoetin alfa injection in the darbepoetin group. These restrictions do not apply to rescue therapy.

- ✓ Correction cohort: Concomitant use is prohibited from 8 weeks prior to the first day of the screening period to completion of blood sampling for haematology tests on the final day of the treatment period.
- ✓ Conversion cohort: Concomitant use is prohibited from the first day of the treatment period to completion of blood sampling for haematology tests on the final day of the treatment period.

(2) Testosterone enanthate and mepitiostane

Concomitant use is prohibited from 8 weeks prior to the first day of the screening period to completion of blood sampling for haematology tests on the final day of the treatment period.

(3) Blood transfusion

Prohibited from 8 weeks prior to the first day of the screening period to completion of blood sampling for haematology tests on the final day of the treatment period. These restrictions do not apply to rescue therapy.

Rationale

(1) – (3) Medications and therapies considered likely to affect evaluation of MT-6548 efficacy are prohibited for concomitant use.

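### The exclusion windows for thrombosis, stroke/acute coronary syndrome and bleeding end on the first day of screening, leaving up to 42 days before treatment uncovered

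*Protocol*

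**What the plan says.** Three exclusions in Protocol 3.3, repeated in the Protocol Summary, count back from the first day of screening:

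- (12): "Patients with incidence or relapse of deep vein thrombosis or pulmonary embolism within 12 weeks prior to the first day of the screening period".
- (10), first sentence, with the same anchor at the start of screening: "Patients with cerebrovascular disorders or acute coronary syndromes (hospitalization for unstable angina or myocardial infarction, etc.) within 12 weeks prior to the first day".
- (2): "Patients with active haemorrhaging or exsanguination within 8 weeks prior to the first day of the screening period".

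Screening then continues up to the first treatment day. Section 5.2 states: "Maximum screening period time is 6 weeks". Section 3.4 repeats the limit: "the maximum time from the first day of the screening period to the first day of the treatment period is 6 weeks".

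Other rules do reach into this interval. Exclusion (7), on blood pressure, applies "during the screening period or on the first day of the treatment period". Exclusions (6) and (8) cover the screening period, and (9) runs from consent. Exclusions (3) and (4), on transfusion and on testosterone enanthate/mepitiostane, have the same pre-screening anchor as the three above, but section 8.5.1 continues them. The entry for the two drugs reads "prohibited from 8 weeks prior to the first day of the screening period to completion of blood sampling for haematology tests", and that ban lasts until the end of treatment. Transfusion is barred over the same span.

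The rationale under 3.3 gives patient safety and ethics as the reason for (5) to (15), and protection of the efficacy evaluation as the reason for (1) to (4).

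**The concern.** A rule meant to keep recent events out of the trial excludes the older event and passes the fresher one. A patient with a pulmonary embolism 11 weeks before screening is excluded. A patient with one in week 3 of screening meets none of the three windows.

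The stake is mainly safety. Criteria (10) and (12) protect patients about to start a haemoglobin-raising drug, and the weeks nearest the first dose are the ones left out. Nothing in the rationale explains that. Comparable windows elsewhere in the protocol are continued past the start of screening, so this looks like a drafting gap rather than a choice.

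For bleeding the stake is smaller. A bleed during screening can lower the haemoglobin values that decide eligibility and stratum, but other criteria catch part of this.

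**Working it through.** The check is calendar arithmetic. The plan states no figure of its own to reproduce.

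**Inputs**
- Look-back L: 12 weeks = 84 days for (10) first sentence and (12); 8 weeks = 56 days for (2) (Protocol 3.3).
- Screening length S: at most 6 weeks = 6 × 7 = 42 days (Protocol 3.4 and 5.2). Lengths of 2 and 4 weeks are assumptions, used to show the range.

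**Formulas**, counting days back from the first treatment day:
- not covered by the window: 0 to S
- excluded by the window: S to S + L

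| Screening | Not covered | Excluded, (10) and (12) | Excluded, (2) |
|---|---|---|---|
| 2 weeks (assumed) | last 14 days | 14 to 14 + 84 = 98 | 14 to 14 + 56 = 70 |
| 4 weeks (assumed) | last 28 days | 28 to 28 + 84 = 112 | 28 to 28 + 56 = 84 |
| 6 weeks (maximum) | last 42 days | 42 to 42 + 84 = 126 | 42 to 42 + 56 = 98 |

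Example at maximum screening: an embolism 17 weeks before treatment (119 days) lies between 42 and 126 and excludes. One a week before treatment (7 days) lies in the last 42 days and does not. The gap is half as long as the 12-week window (42/84) and three quarters as long as the 8-week window (42/56).

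**Does another provision make the event an exclusion?**
- Exclusion (10), second sentence, has no time limit. Hospitalisation for acute coronary angioplasty or cardiac failure during screening therefore excludes. It does not name stroke, thrombosis, bleeding, or a coronary syndrome managed without angioplasty.
- Exclusion (5) removes patients judged likely to need rescue at once. This may catch a serious bleed, by judgement.
- Exclusion (21) is general discretion; its rationale refers to safety reasons other than those already listed.
- Section 8.2.3 requires test results to be reviewed and suitability determined before treatment, but names no such event.
- Sections 9.2.4.2 and 11.1 require serious events from consent onward to be reported and acted on. Reporting is not exclusion.
- Inclusion (6) and (7) set haemoglobin ranges on the mean of the latest two tests and require them to differ by less than 1.5 g/dL. With the transfusion ban, they catch a bleed that shifts haemoglobin materially between tests or needs transfusion. They miss a smaller fall, or a bleed before both tests, if the mean stays in range.
- Re-screening (3.4) would bring an earlier screening event inside the window only if it sets a new first screening day, which the text does not say.

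None of these makes a thrombosis, a stroke or a non-angioplasty coronary syndrome during screening a stated exclusion.

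**The case against.** The strongest reply is that these are conspicuous events and several safeguards stand before the first dose. The investigator must judge suitability, serious events from consent go to the sponsor, and (5) and (21) allow exclusion. Few investigators would start treatment in a patient with a fresh embolism or stroke.

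Much of this stands, and it limits four stronger readings.

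- A reader might infer that discretion under (21) is the only protection. The suitability determination, the reporting duty and exclusion (5) contradict that.
- A reader might infer that coronary events in screening are wholly uncovered. The second sentence of (10) covers part of them, precisely because it carries no window.
- A reader might infer that a screening bleed biases the efficacy result. The documents do not support this. Inclusion (6) and (7) and the transfusion ban screen out many such patients. Those who enter are randomised 1:1 within haemoglobin strata, and baseline haemoglobin is a covariate in the primary model, so spontaneous recovery is not expected to favour one arm. Exclusion (2) could also be read as meaning current bleeding, although the 8-week window attached to it makes that doubtful.
- A reader might extend the point to the dialysis look-back in inclusion (4). That criterion also requires that dialysis not be expected during treatment, and starting continuous haemodialysis or peritoneal dialysis is a withdrawal criterion (12.1). No change is argued there.

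What the reply does not do is make the written rule coherent. Each safeguard is discretionary, indirect or a reporting step, and may be applied differently from site to site.

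**Conclusion.** The point holds for (12) and the first sentence of (10), and with less consequence for (2). As written, up to 42 days before the first treatment day fall outside the windows, so an older event excludes and a more recent one does not. This conflicts with the stated rationale and with the way (7) and section 8.5.1 treat the same interval.

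The 42 days are a maximum and shrink with shorter screening. The conclusion rests on the literal wording of the windows. The documents do not give the number of patients affected; it is probably small. No effect on power, error rate or the primary comparison is shown. It is a wording defect in an eligibility rule, mainly of safety relevance, and worth correcting because the correction is cheap.

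**What to change.** Reconcile the end of the windows in exclusions (10) first sentence, (12) and (2) with the start of treatment, so that the screening period is included. Make the change in section 3.3 and in the Protocol Summary. Leave the 8- and 12-week look-back lengths and inclusion (4) as they are.

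The wording has to be drafted. Section 8.5.1 is a precedent for continuing a window past the first screening day, but its text runs to the final treatment day and cannot be copied unchanged.

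The cost is a wording amendment and a few additional screen failures among patients with an event during screening. No visit or test is added.

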3.4 Re-testing/re-screening

(1) Re-testing

Re-testing during the screening period may be performed at the discretion of investigators/subinvestigators for subjects who did not meet inclusion criteria, or who met exclusion criteria, for reasons such as laboratory values (Hb, eGFR, serum ferritin, TSAT, folic acid, vitamin B₁₂, AST, ALT, or total bilirubin) or blood pressure.

Subjects with blood pressure measurements on the first day of the treatment period which meet exclusion criteria may be re-tested at the discretion of investigators/subinvestigators, and processed for treatment period initiation if they no longer meet exclusion criteria.

However, the maximum time from the first day of the screening period to the first day of the treatment period is 6 weeks.

(2) Re-screening

Re-screening may be performed at the discretion of investigators/subinvestigators if subjects who did not meet inclusion criteria, or who met exclusion criteria, for reasons such as laboratory values (Hb, eGFR, serum ferritin, TSAT, folic acid, vitamin B₁₂, AST, ALT, or total bilirubin), blood pressure, or blood pressure on the first day of the treatment period, may have become eligible for the study due to natural course or drug treatment.

However, re-screening may only be performed once for any given subject.

4. Explanations to subjects and consent

4.1 Informed consent forms and written information

Study investigators will draft informed consent forms and written information for patients. These will be either a single form, or a set of forms, and will be revised as required.

Authored or revised consent forms will be submitted to study sponsor and approved by the Institutional Review Board (IRB) prior to study initiation.

4.2 Content of written information

Written information for subjects must contain at least the following items:

- (1) The study is for research purposes.
- (2) Study objectives
- (3) Names, titles, and addresses of investigators and subinvestigators.
- (4) Study methodology (trial aspects, subject inclusion criteria, and probabilities of being assigned to different study groups).
- (5) Expected clinical benefits, risks, and inconveniences (subjects must also be informed if there are no expected benefits for them).
- (6) If enrolling a patient into the trial, explanation of other therapeutic options for the patient and expected risks/rewards associated with these.
- (7) Expected period of study participation for the subject.
- (8) Participation in the study is purely voluntary, and the subject or his/her agent may rescind agreement to participate at any time. If the subject determines not to participate in the study or withdraws consent, he/she will not be disadvantaged in anyway, and will not forego any benefits from not participating.
- (9) Study monitors, auditors, IRB members, and regulatory authorities may view source documents from the study. In this event, subject confidentiality will be preserved. The subject or his/her agent consents to this viewing of source documents by signing (or printing name and affixing personal seal) the consent form.
- (10) Subject confidentiality will be preserved even if study results are published.
- (11) Contact information for consultations with the study center for when subjects wish to learn more information about the study or their rights, or for when study-related damage to health occurs.
- (12) Financial reimbursements or treatments available to subjects in the event of damage to health resulting from the study.
- (13) Types of IRBs that will investigate and determine issues related to appropriate performance of the study, types of issues which fall under IRB purview, and other study-related issues concerning the IRB.

- (14) Planned number of subjects in the study.
- (15) If any information comes to light which may affect the willingness of the subject or his/her agent to continue study participation, that information will be rapidly shared with the subject or his/her agent.
- (16) Conditions and reasons leading to study withdrawal.
- (17) Details of any costs to be borne by the subject, if applicable.
- (18) Details of any money to be paid to the subject, if applicable (agreements for determining amounts, etc.)
- (19) Behaviors or rules to be followed by the subject.
- (20) Other necessary items or information related to the study.

4.3 Method of obtaining consent

- (1) Prior to initiating study, the investigator/subinvestigator will hand the informed consent forms and written information approved by the IRB to each patient in person, and conduct a full explanation. Clinical coordinators may also perform supplementary explanations. Explanations will be based on written information for the study and use as simple language as possible to ensure patient understanding. All patient questions will be answered fully. After confirming that the patient understands fully, he/she may freely grant informed consent for participation in the study in writing.
- (2) The informed consent form will be signed (or names printed and personal seals affixed) and dated by both the patient and the investigator/subinvestigator who performed the explanation. If clinical coordinators performed supplementary explanations, he/she will also sign (or print name and affix personal seal) and date the form.
- (3) If the patient is incapable of reading the written information, the investigator/subinvestigator will arrange for a fair witness to be present when performing the explanation and obtaining consent. In this case, the witness will also sign (or print name and affix personal seal) and date the consent form.
- (4) Before each subject begins participation in the study, the investigator/subinvestigator will issue hand him or her a signed (or names printed and personal seals affixed) and dated copy of the informed consent forms and written information. Originals of the consent forms will be stored at each study center in accordance with that center's regulations.
- (5) The date of informed consent will be recorded on each CRF.

